There is a rare chance that epacadostat could cause an increase in serotonin levels in the brain that might trigger Serotonin Syndrome when administered in combination with other serotonergic agents. This syndrome has been most closely associated with use of MAOIs, meperidine, linezolid, or methylene blue; all of these agents are prohibited during the study. Serotonin reuptake inhibitors (SSRIs) and serotonin/norepinephrine reuptake inhibitors (SNRIs) are permitted in the study. Serotonin syndrome usually manifests with autonomic changes, mental status changes, and neurological findings. Mild, moderate, and severe signs and symptoms of SS are summarized in table below and should be evaluated in the context of possible comorbid conditions as well. The following procedures will be implemented if participants exhibit the signs/symptoms of SS described in the following table:

- Immediately interrupt epacadostat or matching placebo administration. Administration of pembrolizumab may continue.
- Immediately interrupt any SSRI or SNRI administration.

Provide appropriate medical management of the participant until all signs/symptoms are resolved (e.g., IV fluids and/or sympathomimetic amines for hypotension, benzodiazepines for agitation, administration of 5-hydroxytryptamine antagonists such as cyproheptadine).

If participant chooses to remain in the study, restart treatment with epacadostat or matching placebo after the SSRI or SNRI has been discontinued, no sooner than 5 half-lives have elapsed for the specific SSRI or SNRI in question, and after resolution of signs/symptoms of SS. The SSRI or SNRI dosing MAY NOT be restarted.

If participant chooses to withdraw from the study, or must restart treatment with SSRI or SNRI, the participant should be scheduled for a follow-up visit. Treatment with SSRI or SNRI may be initiated 2 weeks after resolution of signs and symptoms of SS.

Additionally, sites should contact the Incyte Clinical Director if Serotonin Syndrome is suspected.

Table 4-7: Sign and Symptoms of Serotonin Syndrome

4.3.4 Seriousness	4.3.5 Autonomic signs	4.3.6 Neurological signs	4.3.7 Mental status	4.3.8 Other
4.3.9 Mild	Afebrile or low-grade fever	Intermittent tremor	Restlessness	
	Tachycardia	Akathisia	Anxiety	
	Mydriasis	Myoclonus		
	Diaphoresis or shivering	Mild hyperreflexia		
4.3.10 Moderate	Increased Tachycardia	Hyperreflexia	Easily startled	Rhabdomyolysis
	Fever (up to 41 °C)	Inducible clonus	Increased confusion	Metabolic acidosis

	Diarrhea with hyperactive bowel sounds	Ocular clonus (slow continuous lateral eye movements)	Agitation and hypervigilance	Renal Failure
	Diaphoresis with normal skin color	Myoclonus		Disseminated intravascular coagulopathy (secondary to hyperthermia)
4.3.11 Severe	Temperature often more than 41 0C (Secondary to increased tone)	Increased muscle tone (lower limb > upper)	Delirium	As above
		Spontaneous clonus	Coma	
		Substantial myoclonus or hyperreflexia		

¹ Boyer EW, Shannon M. The serotonin syndrome. New Engl J Med 2005;352: 1112-1120.

Dose Modification versus Dose Interruption

Epacadostat, pembrolizumab and tavo-EP may be held for up to 6 weeks as clinically indicated or required due to treatment associated AEs but dose reductions are not permitted.

Dosing interruptions of all agents may be permitted in the case of medical/surgical events or logistical reasons not related to study therapy (eg, elective surgery, unrelated medical events, subject vacation, and/or holidays). Subjects should be placed back on study therapy within 6 weeks of the scheduled interruption. The reason for interruption should be documented in the subject's study record.

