4.3.3 Treatment Modification – All Agents

Adverse events associated with treatment on study may be immune-related or not immune-related. Immune-related AEs (irAEs) may be predicted based on the nature of the compounds, their mechanism of action, and reported experience with immunotherapies that have a similar mechanism of action. Special attention should be paid to AEs that may be suggestive of potential irAEs. An irAE can occur shortly after the first dose or several months after the last dose of treatment. If an irAE is suspected, efforts should be made based on the investigator's clinical judgment to rule out neoplastic, infectious, metabolic, toxins, or other etiologic causes prior to labeling an AE as an irAE.

In some circumstances, it may be necessary to temporarily interrupt pembrolizumab, tavo-EP or epacadostat as a result of AEs that may have an unclear relationship to any individual study drug. If an interruption for an adverse event is necessary and the causative agent cannot be identified, all agents should be interrupted. Immune-related adverse events may also be attributable to epacadostat alone, pembrolizumab alone, tavo-EP, alone or the combination of two or three of these agents. If the event is clearly related to one of the agents, follow the instructions specific for that agent. If the event is related to more than one agent, follow the action taken instructions for each causative agent.

General supportive care recommendations to manage irAEs are detailed in *Table 4-4*. Additional treatment modification recommendations may be found in subsequent sections, in the pembrolizumab package insert, and in the investigator's brochures for epacadostat and tavo-EP.

Table 4-4: General Guidelines for Immune-Related Adverse Events

irAE Toxicity Grade	Withhold/Discontinue Agent(s)	Action Taken With Respect to Agent(s)	Supportive Care
Grade 1	No action.	Not applicable.	Provide symptomatic treatment.

Grade 2	May withhold agent per investigator's discretion.	Not applicable. Investigators discretion.	Consider systemic corticosteroids in addition to appropriate symptomatic treatment.

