Grade 3	Withhold or discontinue agent(s). Discontinue if unable to reduce corticosteroid dose to < 10 mg/day of prednisone or equivalent within 6 weeks of toxicity.	Return to treatment if improves to Grade 1 or resolves within 6 weeks. If AE resolves within 4 weeks, subject may restart at the same dose and schedule for epacadostat. For an AE that does not resolve within 4 weeks, agent(s) should be reduced 1 dose level. If AE does not resolve within 6 weeks, study treatment with agent(s) should be discontinued or discussed with principal investigator.	Systemic corticosteroids are indicated in addition to appropriate symptomatic treatment. May use 1-2 mg/kg prednisone or equivalent per day. Steroid taper should be considered once symptoms improve to ≤ Grade 1 and tapered over at least 4 weeks in most cases.
Grade 4	Discontinue agent(s).	Not applicable. Any exceptions require principal investigator approval.	Systemic corticosteroids are indicated in addition to appropriate symptomatic treatment. May use 1-2 mg/kg prednisone or equivalent per day. Steroid taper should be considered once symptoms improve to ≤ Grade 1 and tapered over at least 4 weeks in most cases.

Any interruptions of > 2 weeks or for LFT abnormalities must be discussed with the principal investigator before resuming treatment. Treatment with epacadostat, pembrolizumab, and tavo-EP should be withheld for drug-related Grade 4 hematologic toxicities, non-hematological toxicity ≥ Grade 3 (including laboratory abnormalities), and severe or life-threatening AEs.

Discontinuation Rules and Procedures for Specific Immune-Related Adverse Events Associated with Epacadostat and Pembrolizumab

Supportive care measures for the management of adverse events with potential immunologic etiology that are, in the judgment of the investigator, at least possibly associated with pembrolizumab and/or epacadostat are outlined in **Table 4-5** below and **Table 4-6** for pembrolizumab infusion-related reactions. For AEs listed in **Table 4-5** and **Table 4-6**, follow the guidelines in **Table 4-5**, and **Table 4-6**. For AEs not listed in **Table 4-5** or **Table 4-6**, follow the guidelines in **Table 4-4**. For each disorder listed in **Table 4-5**, and **Table 4-6** attempts should be made based in the investigator's clinical judgment to rule out other causes such as metastatic disease or bacterial or viral infection, which might require additional supportive care.

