	3	Interrupt epacadostat and pembrolizumab. When diarrhea resolves to baseline, resume pembrolizumab and restart epacadostat at a reduced dose. Monitor subjects for signs and symptoms of enterocolitis (such as diarrhea, abdominal pain, mucus or blood in stool, with or without fever) and of bowel perforation (such as peritoneal signs and ileus). In symptomatic subjects, rule out infectious etiologies and consider endoscopic evaluation for persistent or severe symptoms. For recurrent or persistent Grade 3 diarrhea, consider further dose reduction of epacadostat, or discontinuation of pembrolizumab and epacadostat.
	4	Discontinue epacadostat and pembrolizumab
Pneumonitis	2	Interrupt epacadostat and pembrolizumab and initiate systemic corticosteroids. Taper as necessary. May return to study treatment if condition improves to \leq Grade 1. Permanently discontinue if toxicity does not resolve within 12 weeks of last dose or if subject shows inability to reduce corticosteroid to \leq 10 mg prednisone or equivalent per day within 12 weeks.

Adverse Event	CTCAE v4.03 Grade	Action Taken
	3 or 4	
Permanently discontinue epacadostat and pembrolizumab. Immediately treat with intravenous corticosteroids. Administer additional anti-inflammatory measures, as needed.
 
Add prophylactic antibiotics for opportunistic infections in the case of prolonged steroid administration.

Type I diabetes mellitus (TIDM; if new onset, including diabetic ketoacidosis [DKA]) or \geq Grade 3 hyperglycemia, if associated with ketosis (ketonuria) or metabolic acidosis (DKA)	Newly onset TIDM or Grade 3 or 4	
Insulin replacement therapy is recommended for Type I diabetes mellitus and for Grade 3-4 hyperglycemia associated with metabolic acidosis or ketonuria.
 
Evaluate subjects with serum glucose and a metabolic panel, urine ketones, glycosylated hemoglobin, and C-peptide.
 
Once serum glucose is stabilized, pembrolizumab, tavo-EP and epacadostat should restart at the same dose if the episode is thought to be unrelated to treatment. If the episode is related, resume treatment with a one level dose reduction of epacadostat.

Hypophysitis	2	
Hold pembrolizumab and epacadostat. Treat with oral corticosteroids. When symptoms improve to \leq Grade 1, steroid taper should be started and continued over no less than 4 weeks. Replacement of appropriate hormones may be required as the steroid dose is tapered.

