	3 or 4	
Discontinue epacadostat and pembrolizumab. Treat with an initial dose of IV corticosteroids followed by oral corticosteroids. When symptoms improve to Grade 1 or less, steroid taper should be started and continued over no less than 4 weeks. Replacement of appropriate hormones may be required as the steroid dose is tapered.

Hyperthyroidism or hypothyroidism	2	
Thyroid disorders can occur at any time during treatment. Monitor subjects for changes in thyroid function (at the start of treatment, periodically during treatment, and as indicated based on clinical evaluation) and for clinical signs and symptoms of thyroid disorders.
 
In hyperthyroidism, nonselective beta-blockers (eg, propranolol) are suggested as initial therapy.
 
In hypothyroidism, thyroid hormone replacement therapy, with levothyroxine or liothyronine, is indicated per standard of care.

Adverse Event	CTCAE v4.03 Grade	Action Taken
	3 or 4	
In hypothyroidism, thyroid hormone replacement therapy, with levothyroxine or liothyronine, is indicated per standard of care.
 
In hyperthyroidism, treat with an initial dose of IV corticosteroid followed by oral corticosteroids. When symptoms improve to \leq Grade 1, steroid taper should be started and continued over no less than 4 weeks.
 
Replacement of appropriate hormones may be required as the steroid dose is tapered. Once hyperthyroidism has resolved and steroids tapered, subject may resume epacadostat, pembrolizumab and tavo-EP or permanently discontinue at the discretion of the investigator.

Hepatic	2	
Hold pembrolizumab and epacadostat. Monitor liver function tests more frequently until returned to baseline values (consider weekly or twice weekly if steroids are not initiated). Treat with IV or oral corticosteroids.

	3 or 4	
Permanently discontinue pembrolizumab and epacadostat if related to these agents. Treat with intravenous corticosteroids. When liver chemistry tests improve to \leq Grade 1, a steroid taper should be started and continued over no less than 4 weeks. If unrelated to pembrolizumab, treatment with pembrolizumab and epacadostat may be resumed once steroids have been discontinued.

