Other AEs	4	In general, epacadostat and pembrolizumab should be discontinued. Treatment with epacadostat and pembrolizumab may only be restarted after consideration of the benefit versus the risk and the approval of the principal investigator.

Procedures for Other Immune-Mediated Adverse Reactions, Including Ocular Manifestations

Epacadostat and pembrolizumab should be permanently discontinued for severe (Grade 4) irAEs. Systemic corticosteroids treatment should be initiated at a dose of 1 to 2 mg/kg per day of prednisone or equivalent for severe irAEs.

Corticosteroid eye drops should be administered to subjects who develop uveitis, iritis, or episcleritis. Epacadostat and pembrolizumab should be permanently discontinued for immune-mediated ocular disease that is unresponsive to local immunosuppressive therapy.

Dose modification and toxicity management of infusion-reactions related to pembrolizumab

Pembrolizumab may cause severe or life threatening infusion-reactions including severe hypersensitivity or anaphylaxis. Signs and symptoms usually develop during or shortly after drug infusion and generally resolve completely within 24 hours of completion of infusion. Dose modification and toxicity management guidelines on pembrolizumab associated infusion reaction are provided in **Error! Reference source not found.**

Table 4-6: Pembrolizumab Infusion Reaction Dose Modification and Treatment Guidelines

NCI CTCAE Grade	Treatment	Premedication at Subsequent Dosing
Grade 1 Mild reaction; infusion interruption not indicated; intervention not indicated	Increase monitoring of vital signs as medically indicated until the participant is deemed medically stable in the opinion of the investigator.	None

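### Table 4-5, grade 3-4 Hepatic and Renal rows: the condition for resuming both drugs names only pembrolizumab, so a grade 3 event attributed to epacadostat alone is told to stop permanently and is also allowed to resume.

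*Combined protocol and SAP*

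**What the plan says.** In Section 4.3.3, the grade 3 or 4 entries of Table 4-5 for Hepatic events and for Renal failure or nephritis share the same two conditions. The stop sentence is "Permanently discontinue pembrolizumab and epacadostat if related to these agents". After the steroid instructions comes the resume sentence: "If unrelated to pembrolizumab, treatment with pembrolizumab and epacadostat may be resumed once steroids have been discontinued".

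The introduction to Section 4.3.3 accepts that causality can lie with one drug: "Immune-related adverse events may also be attributable to epacadostat alone, pembrolizumab alone, tavo-EP, alone or the combination" of several. It sends an event clearly due to one drug to that drug's own instructions. It also points outside the protocol: "Additional treatment modification recommendations may be found in subsequent sections, in the pembrolizumab package insert, and in the investigator's brochures for epacadostat and tavo-EP". The text introducing Table 4-5 describes its scope as events at least possibly associated with one drug and/or the other.

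Two further rules bear on resumption: "Any interruptions of > 2 weeks or for LFT abnormalities must be discussed with the principal investigator before resuming treatment", and, for grade 4, "Epacadostat and pembrolizumab should be permanently discontinued for severe (Grade 4) irAEs".

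**The concern.** The two sentences should divide the cases between them: one set stops, the rest may resume. They do not, because the first tests causality for two drugs and the second for pembrolizumab only, although it restarts both. An event attributed to epacadostat alone falls on both sides.

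At stake is the management of an individual patient after a severe liver or kidney event. One sentence takes both drugs away permanently; the other allows both back, including the drug thought to have caused the event. Those making the decision find no settled rule in the row.

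**Working it through.** No figure in the plan needs reproducing. The check compares the two conditions case by case, then sizes the exposure.

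**1. Reading of the stop sentence.** *These agents* could mean either drug or both jointly. Either drug is the sensible reading. The scope text uses and/or. The grade 3-4 Myocarditis row uses the same phrase with no resume sentence, so a joint reading would leave severe myocarditis due to one drug without that row's stop rule.

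**2. Four attribution cases.** Section 11.4 classes an event as related or unrelated to the investigational drug or intervention. Applying that scale to each drug is a step taken here, justified by the Section 4.3.3 statement on single-drug attribution.

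| Event related to | Stop sentence | Resume sentence | Current result | With aligned conditions |
|---|---|---|---|---|
| Both drugs | applies | does not apply | stop | stop |
| Pembrolizumab only | applies | does not apply | stop | stop |
| Epacadostat only | applies | applies | stop, and may resume | stop |
| Neither | does not apply | applies | may resume | may resume |

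One case of four is open. For immune-related events it is open at grade 3 only, since grade 4 is settled by the permanent-discontinuation rule.

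**3. Does other text settle it?**
- The single-drug rule in Section 4.3.3 points to drug-specific instructions, which these two rows lack for epacadostat.
- The text after Table 4-4 requires a discussion but does not state its outcome. It also sends events listed in Table 4-5 to that table, so Table 4-4 does not displace the row.
- The Rechallenge entry of Table 11-1 requires advance approval for certain serious events, as per the dose modification guidelines, which leads back to this table.
- Section 11.5 leaves rechallenge to the investigator's view of safety and ethics.
- The diabetes row shows matched branches are possible, the first of them an unchanged restart: "if the episode is thought to be unrelated to treatment. If the episode is related, resume treatment with a one level dose reduction of epacadostat".

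**4. Timing.** Both rows require a steroid taper of at least 4 weeks once the event improves to grade 1 or less, and resumption only after steroids end. The text on dose interruption limits a hold to 6 weeks. So 6 − 4 = 2 weeks remain for improvement. Any resumption follows an interruption of at least 4 weeks, which exceeds 2 weeks, so discussion with the principal investigator is required in both rows.

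**5. Patients exposed to epacadostat.** Planned numbers are 12 in the lead-in, 15 in Arm A Stage 1 and 13 more in Arm A Stage 2. Lead-in patients may be counted in Arm A.
- Stage 2 opens, no overlap: 12 + 15 + 13 = 40. Full overlap: 15 + 13 = 28.
- Stage 2 does not open, no overlap: 12 + 15 = 27. Full overlap: 15.

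Stage 2 needs at least 3 responses in 15. For one arm at the null rate of 15%, the chance of 2 or fewer is 0.85^15 + 15 × 0.15 × 0.85^14 + 105 × 0.15² × 0.85^13 = 0.087 + 0.231 + 0.286 = 0.60, so the lower figures are realistic.

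**6. Expected epacadostat-only events.** The documents give no rate, so rates are assumed. The reference point is grade 3 or higher treatment-related AST increase with epacadostat 100 mg BID plus pembrolizumab (Section 1.2.2): 2 of 18 + 99 = 117, or 1.7%. It is not a rate for epacadostat alone.

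| Assumed rate | 15 patients | 40 patients |
|---|---|---|
| 0% | 0 | 0 |
| 0.5% | 0.08 | 0.2 |
| 2/117 = 1.7% | 0.26 | 0.68 |
| 5% | 0.75 | 2.0 |

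These counts are not reduced for the requirement to improve within about 2 weeks, so they overstate how often resumption would arise.

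**The case against.** The stop sentence is mandatory and the resume sentence permissive, so a careful reader may hold that a permission cannot undo a permanent stop already triggered. That is reasonable, but the row does not say it, and the resume sentence is the row's only written condition for restarting either drug. Epacadostat causality is absent from it.

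Oversight is also substantial. Drug-related non-hematological toxicity of grade 3 or higher calls for withholding all three agents, resumption must be discussed with the principal investigator, and the coordinating-centre investigator chairs the study across sites. This stands. A reader might infer that sites would quietly act in opposite ways; these provisions make that unlikely.

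A reader might also infer that restarting epacadostat after a grade 3 event is improper in itself. The documents do not support this. Table 4-4 says for grade 3: "If AE resolves within 4 weeks, subject may restart at the same dose and schedule for epacadostat", and the grade 3 diarrhea row of Table 4-5 allows a restart at a reduced dose.

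A third tempting inference is that a pembrolizumab-only event has no instruction. That needs the joint reading of *these agents*. The catch-all toxicity row of Table 4-5 does join the two drugs with a plain *and*, but the and/or scope text and the Myocarditis row weigh against a joint reading here.

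Finally, the epacadostat brochure was not available for this check and may hold guidance that fills the gap.

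**Conclusion.** The point stands as a minor patient-safety correction confined to one attribution case in two rows: a grade 3 hepatic or renal event attributed to epacadostat alone. The row both stops and allows resumption, and the permission extends to the suspected drug.

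Few patients are likely to be affected, possibly none: under the assumed rates of 0% to 5%, 0 to 2 of the 15 to 40 exposed. The conclusion rests on reading *these agents* as either drug, on attribution being made drug by drug, and on the protocol text without the brochures or package insert.

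A reader might infer consequences for dose finding or efficacy. The documents do not support that: the lead-in rules count toxicities when they occur, whatever is done about resumption, and the response rate is calculated on all treated subjects. No endpoint or analysis is affected.

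**What to change.** In both rows, change the resume condition to *If unrelated to both pembrolizumab and epacadostat*. For clarity, change the stop condition to *if related to either agent*. Each of the four cases then meets exactly one sentence. Arm B is unaffected in substance, because those patients do not receive epacadostat.

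The documents do not show whether the sponsor meant pembrolizumab to continue after an epacadostat-only event. If it did, it should add a separate instruction that pembrolizumab alone may resume, and check it against the epacadostat brochure.

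The cost is two short phrases in each of two rows, with no effect on enrolment or analysis. The clinical downside is that, without the added instruction, a patient with an epacadostat-only event loses the option of resuming pembrolizumab.

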4.3.2 Dose Modifications and Management of Toxicity

Dose modifications are permitted in Cycle 1 only in the event of a DLT.

Dose modifications of epacadostat will be made per the dose escalation table.

1. If dose reduction of epacadostat is necessary:

- The dose should be reduced stepwise based on the dose escalation table. The patient should be monitored for approximately 10 to 14 days at each dose level.

Treatment or visit delays for public holidays or weather conditions do not constitute a protocol violation. After cycle 2, patients who have benefit are allowed to request treatment interruptions for personal reasons up to three weeks. Longer treatment interruptions must be approved by the PI and the drug sponsor.

The following dose modification rules will be used with respect to potential toxicity. Toxicity will be assessed according to the NCI Common Terminology Criteria for Adverse Events Version 4.03 (CTCAE v4.03).

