Myocarditis	2	
Hold pembrolizumab and epacadostat until resolution to Grade 0. Monitor symptoms daily, hospitalize. Promptly start IV methylprednisolone 2 to 4 mg/kg/day or equivalent after Cardiology consultation has determined whether and when to complete diagnostic procedures including a cardiac biopsy. Once the patient is improving, gradually taper steroids over \geq28 days and consider prophylactic antibiotics, antifungals, or anti-PJP treatment (refer to current NCCN guidelines for treatment of cancer-related infections [Category 2B recommendation]). If toxicity rapidly improves to Grade 0, then the decision to reinitiate study drug/study regimen will be based upon treating physician's clinical judgment and after completion of steroid taper. If toxicity does not rapidly improve, permanently discontinue pembrolizumab and epacadostat.

Adverse Event	CTCAE v4.03 Grade	Action Taken
	3 or 4	Permanently discontinue pembrolizumab and epacadostat if related to these agents. Monitor symptoms daily, hospitalize. Promptly start IV methylprednisolone 2 to 4 mg/kg/day or equivalent after Cardiology consultation has determined whether and when to complete diagnostic procedures including a cardiac biopsy. Once the patient is improving, gradually taper steroids over \geq 28 days and consider prophylactic antibiotics, antifungals, or anti-PJP treatment (refer to current NCCN guidelines for treatment of cancer-related infections [Category 2B recommendation]).
Renal failure or nephritis	2	Treat with oral corticosteroids.
	3 or 4	Permanently discontinue pembrolizumab and epacadostat if related to these agents. Treat with systemic corticosteroids. When severity of the event improves to \leq Grade 1, steroid taper should be started and continued over no less than 4 weeks. If unrelated to pembrolizumab, treatment with pembrolizumab and epacadostat may be resumed once steroids have been discontinued.
Any toxicity, if clinically significant and not manageable by supportive care	2 or 3	Interrupt epacadostat and pembrolizumab if toxicity is attributed to epacadostat and pembrolizumab. When toxicity resolves to \leq Grade 1, resume pembrolizumab and epacadostat. For recurrent or persistent Grade 2 or 3 toxicity that is clinically significant and not manageable with supportive care, consider further dose reduction of epacadostat or epacadostat and pembrolizumab discontinuation.

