5.2 Safety Stopping Rules

Clinical evaluations including laboratory and clinical safety assessments will be performed at 3-week intervals for patients who are actively receiving treatment on study. For patients in the follow-up portions of the study who are not actively receiving therapy, evaluations will be performed at 12-week intervals. Safety will be assessed during the study by documentation of adverse events (AEs), clinical laboratory tests, physical examination, vital sign measurements, and Eastern Cooperative Oncology Group (ECOG) performance status.

Lead-In Period and De-Escalation

1. If, at any time, 2 or more of the first 6 safety-evaluable patients experience grade 3 or higher treatment-associated adverse events within the first 30 days of initiation of treatment, then no further patients will be enrolled at the current dose level.
2. After 6 patients have been enrolled on study, enrollment will be halted for 30 days for completion of lead-in safety analysis. If 0-1 patients experience grade 3 or higher treatment-associated adverse events within the first 30 days of initiation of treatment, then additional patients may be enrolled at the current dose level.
3. If enrollment is halted at any time during the lead-in period due to treatment-associated adverse events, the UCSF DSMB will review all available safety data with the Principal Investigator. Based on this review, study discontinuation or reduction of the epacadostat dose may be recommended. No further patients will be enrolled on study without the approval of the DSMB. If the DSMB allows additional patients to enroll, the lead-in period will be repeated at the new dose level with a maximum of 6 additional patients enrolled prior to follow-up safety analysis. At the discretion of the DSMB, patients who are currently on study may continue treatment at the reduced dose level.
4. Patients who discontinue treatment on study within 30 days of initiation of therapy for reasons other than treatment-associated toxicity will be deemed inevaluable for safety and replaced for safety analysis.

Mid-Study Interim Safety Analysis

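### A blanket ban on dose reductions contradicts the epacadostat reductions in 4.3.2 and Tables 4-4 and 4-5, leaving the restart dose after severe toxicity undefined

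*Combined protocol and SAP*

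**What the plan says.** The paragraph headed Dose Modification versus Dose Interruption closes section 4.3. It lists epacadostat, pembrolizumab and tavo-EP together and lets them be held for up to 6 weeks "as clinically indicated or required due to treatment associated AEs but dose reductions are not permitted". Epacadostat is the first agent named, and there is no exception for it.

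Elsewhere in section 4.3, epacadostat is reduced:

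- Section 4.3.2: "Dose modifications of epacadostat will be made per the dose escalation table". If a reduction is needed, "The dose should be reduced stepwise based on the dose escalation table". In Cycle 1, modification is allowed only after a DLT.
- Table 4-4, Grade 3: "For an AE that does not resolve within 4 weeks, agent(s) should be reduced 1 dose level".
- Table 4-5, Grade 3 diarrhea/colitis: "When diarrhea resolves to baseline, resume pembrolizumab and restart epacadostat at a reduced dose".
- Table 4-5, new-onset type 1 diabetes or ketotic hyperglycemia: "If the episode is related, resume treatment with a one level dose reduction of epacadostat".
- Table 4-5, other clinically significant Grade 2 or 3 toxicity that recurs or persists: "consider further dose reduction of epacadostat or epacadostat and pembrolizumab discontinuation".

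Section 4.3.3 says which of Tables 4-4, 4-5 and 4-6 applies to which adverse event. It does not say whether the tables or the later ban prevail. As context, section 5.2 and the synopsis also foresee reduced dosing after a committee review: "At the discretion of the DSMB, patients who are currently on study may continue treatment at the reduced dose level".

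**The concern.** A site treating a patient whose Grade 3 diarrhea has resolved finds two instructions in the same section. Table 4-5 says to restart epacadostat lower. The ban, read as written, leaves only a full-dose restart or permanent discontinuation. Following either text breaches the other.

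What is at stake is re-exposure after a severe toxicity, and whether sites handle it the same way. Safety of the triplet is the primary objective of the lead-in, where section 4.3.2 also governs what happens to a patient after a Cycle 1 DLT. The problem therefore reaches the dose-finding part of the trial as well as Arm A.

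**Working it through.** This is a check of consistency between instructions. No sample size, power or alpha figure enters it, so there is no figure in the plan to reproduce first.

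**Step 1. Set the instructions side by side.**

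| Situation | Specific text | What the ban leaves | Can both be followed? |
|---|---|---|---|
| 4.3.2, epacadostat reduction judged necessary | Step down Table 4-1 | Hold, same dose, or stop | No |
| Table 4-4, Grade 3 event unresolved at 4 weeks | One level down | Same dose or stop | Only by stopping, which that row also allows |
| Table 4-5, Grade 3 diarrhea, now resolved | Restart epacadostat lower | Same dose or stop | No |
| Table 4-5, treatment-related diabetes, glucose stable | Resume one level lower | Same dose or stop | No |
| Table 4-5, recurrent or persistent Grade 2 or 3 toxicity | Consider reducing or stopping | Stop or continue | Yes, but one of the two offered options is removed |

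The conflict is direct in three rows and partial in the other two.

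**Step 2. Look for a reading that reconciles them.** The ban cannot be confined to pembrolizumab and tavo-EP, because it names epacadostat. It is a complete sentence in the current text, with no precedence rule on either side.

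**Step 3. Find which patients it governs.** Only epacadostat has dose levels (Table 4-1). Arm B receives none (Table 4-2). The contradiction therefore applies to the lead-in and Arm A.

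**Step 4. Size the dose difference.** Table 4-1 gives level -1 = 200 mg, level 0 = 300 mg and level 1 = 600 mg, each BID. The diarrhea row does not name the reduced level; one step is assumed from the stepwise rule in 4.3.2.

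- Level 1 to 0: 2 × 600 = 1200 mg/day falls to 2 × 300 = 600 mg/day. (1200 − 600)/1200 = 50%.
- Level 0 to -1: 2 × 300 = 600 mg/day falls to 2 × 200 = 400 mg/day. (600 − 400)/600 = 33%.
- Level -1: Table 4-1 has no lower step, and nothing says what to do there.

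**Step 5. Minor related wording.** Section 4.6.1.3 speaks of giving tavo-EP in odd-numbered cycles. The synopsis, Table 3-1 and Table 4-2 schedule Days 1, 5 and 8 of every 42-day cycle.

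**The case against.** The best defense is that specific instructions normally override a general one, so most sites would follow the tables. That is a fair forecast of behavior, but the protocol does not say it, and a site should not have to infer which safety instruction is void.

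There are also safeguards. Section 4.3.3 requires discussion with the principal investigator before treatment resumes after an interruption of more than 2 weeks, or after one for liver-test abnormalities. Table 4-4 calls for reduction only after 4 weeks without resolution, so if the drug was withheld from onset, that restart would already be discussed. This weakens the Table 4-4 part of the concern. It does not cover diarrhea that resolves within 2 weeks, and the principal investigator would be reading the same conflicting text. Regular site calls and Study Chair review may catch divergence but do not correct the wording.

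Both readings hold the drug first. That stands: the dispute is about the restart dose, not about whether to interrupt.

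A reader might also infer that the ban contradicts the DSMB rules in section 5.2 and the synopsis, and count these as further conflicts. The documents do not support that. Those rules concern committee decisions on the dose level for a cohort or the study, which can coexist with a ban on reductions by individual investigators. They show only that the plan expects reduced dosing to occur.

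**Conclusion.** The contradiction is real and should be fixed. As written, the ban conflicts with the patient-level epacadostat reductions in 4.3.2, Table 4-4 (Grade 3) and Table 4-5 (Grade 3 diarrhea, related diabetes), and removes an option that Table 4-5 suggests for recurrent or persistent Grade 2 or 3 toxicity. The restart dose in dispute differs by 50% or 33%, assuming a one-level step.

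Three stronger readings are not supported:

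- **That a known number of patients is affected.** With no lead-in overlap, 12 + 15 = 27 patients would receive epacadostat if Arm A stops after Stage 1, and 12 + 28 = 40 if it completes Stage 2; overlap lowers both figures. These count patients treated under the text, not patients who will have a qualifying toxicity. The documents give no basis for the latter.
- **That the Simon design or BORR is compromised.** Nothing in the sample size or the response analysis depends on these instructions, and no such effect is claimed.
- **That tavo-EP is planned at half intensity.** The odd-cycle wording is permissive and visibly garbled. The synopsis, Table 3-1 and Table 4-2 agree against it, and section 4.6.1.4 sends the reader back to Table 3-1. It is a minor correction.

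**What to change.** 1. In Dose Modification versus Dose Interruption, limit the no-reduction sentence to pembrolizumab and tavo-EP. For epacadostat, refer to 4.3.2 and Tables 4-4 and 4-5.
2. In Table 4-4, Grade 3, replace the wording that covers any agent with, for example: *if epacadostat is a causative agent, lower epacadostat by one level of Table 4-1; pembrolizumab and tavo-EP are held or discontinued, never reduced*. The condition matters. It keeps the rule in 4.3.3 of acting on the causative agent, and it avoids directing an epacadostat reduction in Arm B or for an event due to another agent. Add that a patient already at level -1 (200 mg BID) who needs a reduction discontinues epacadostat.
3. Minor: in 4.6.1.3, change the odd-cycle wording so that tavo-EP is given in each cycle, matching the synopsis, Table 3-1 and Table 4-2.

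Cost: one protocol amendment, signed by the investigator and approved by the PRC and the IRB (section 12.4), with approval by participating-site IRBs as well (section 12.11). No patients, visits or assessments are added.
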